2.2 SCREENING EVALUATION

Screening evaluations must be performed within the timeframes indicated below. Screening procedures may be performed on an NIH screening protocol or the UOB 02-C-0159. Imaging studies may also be performed at an outside institution for expedience. If procedures are performed on this treatment protocol, the screening examination must start with the Informed Consent procedure. The investigator is obliged to give the patient thorough information about the study and the study related assessments, and the patient should be given ample time to consider his or her participation. The investigator must not start any study related procedure before ICF is signed and dated by both patient (and impartial witness, if applicable) and investigator.

- To be performed within 2 weeks prior to subject receiving study drug
 - History and physical evaluation
 - Vital signs
 - Performance status
 - EKG
 - Hematology: CBC with differential
 - Biochemistry: BUN or uric acid, creatinine, LDH, total protein, sodium, potassium, calcium, total bilirubin, GGT, albumin, alkaline phosphatase, AST, fasting glucose
 - Fasting serum lipid profile
 - Urinalysis
 - CT chest/abdomen/pelvis and/or CT chest plus MRI abdomen/pelvis, bone scans in patients with known or suspected bone metastases
 - CT Neck in patients with known or suspected metastatic disease in the neck
 - Brain MRI or Brain CT (studies are to be performed with contrast unless renal impairment or allergy prohibits the use of contrast)
 - FDG-PET in patients with known or suspected metastatic disease
 - Serum β HCG (in female patients of childbearing potential)
 - HbA1c, pulmonary function tests (if clinically indicated), pulse oximetry
 - HBV-DNA, HBsAg, HBs Ab, HBc Ab, HCV-RNA-PCR

Abbreviated Title: Phase II everolimus for BHD

Version Date: March 7, 2017

The management guidelines, in Section [3.3.2](#), are provided according to the results of the baseline assessment of viral load and serological markers for hepatitis B.

The management guidelines, in Section [3.3.2](#), are provided according to the results of the baseline assessment of hepatitis C viral load.

For baseline evaluations, please see Section [2.4](#).

2.3 REGISTRATION PROCEDURES

Authorized staff must register an eligible candidate with NCI Central Registration Office (CRO) within 24 hours of signing consent. A registration Eligibility Checklist from the web site (<http://home.ccr.cancer.gov/intra/eligibility/welcome.htm>) must be completed and sent via encrypted email to: NCI Central Registration Office (HOIS) [contact]. After confirmation of eligibility at Central Registration Office, CRO staff will call pharmacy to advise them of the acceptance of the patient on the protocol prior to the release of any investigational agents. Verification of Registration will be forwarded electronically via e-mail to the research team. A recorder is available during non-working hours.

2.4 BASELINE EVALUATION

Baseline procedures need not be repeated if they have been performed within the appropriate screening timeframe (See Section [2.2](#)).

- Height
- Weight
- Thyroid function tests
- Prothrombin time/partial thromboplastin time (PT/PTT)
- Serum β hCG (in female patients of childbearing potential) within 2 weeks.
- CBC with differential.
- Total and direct bilirubin, AST/SGOT, ALT/SGPT, acute care panel, albumin, calcium, magnesium, LDH, amylase, lipase, lipid panel, T3, free thyroxine, TSH
- PFT
- Biopsies (optional) for correlative studies (see Section [5.1](#))
- Obtain archival tumor tissue when available (tissue block and/or up to 30 unstained slides)
- Photographic evaluation of skin lesions (only in patients with BHD- associated cutaneous)

3 STUDY IMPLEMENTATION

3.1 STUDY DESIGN

This is an open label, phase II study to evaluate the efficacy and safety of everolimus therapy in patients with BHD. Up to 16 evaluable patients will be enrolled.

Patients with BHD typically have bilateral, multifocal tumors localized to the kidneys. In general, the growth rates of these tumors is relatively slow and they are not expected to pose a risk of metastatic spread when the size of the tumors is <3cm. Most of these patients have a surgical option (partial nephrectomy) and are less willing to accept side effects than are patients with metastatic disease. Therefore, everolimus will be administered at a starting dose of 5mg PO QD. If the following criteria are met at the time of the first restaging evaluation, the dose will be escalated to 10mg PO QD.

- A) The patient has not had a complete or partial response, and
- B) The patient has not experienced grade 2 or greater toxicity attributable to everolimus

Restaging will be performed approximately every 12 weeks. Treatment can continue for up to 52 weeks in the absence of unacceptable toxicity or disease progression, except in patients with metastatic RCC associated with BHD in whom everolimus will be continued until disease progression or unacceptable toxicity.

All dosages prescribed and dispensed to the patient and all dose changes during the study must be recorded.

3.2 DRUG ADMINISTRATION

The investigator should promote compliance by instructing the patient to take the study drug exactly as prescribed and by stating that compliance is necessary for the patient's safety and the validity of the study. The patient should be instructed to contact the investigator if he/she is unable for any reason to take the study drug as prescribed.

Everolimus should be administered orally once daily at approximately the same time every day, either consistently with or consistently without food.

The tablets should be swallowed whole with a glass of water and should not be chewed or crushed. For patients unable to swallow tablets, the tablet(s) should be dispersed completely in a glass of water (containing approximately 30 mL) by gently stirring until the tablet(s) is fully disintegrated (approximately 7 minutes), immediately prior to drinking. The glass should be rinsed with the same volume of water and the rinse completely swallowed to ensure the entire dose is administered.

If vomiting occurs, no attempt should be made to replace the vomited dose. Patients should be instructed that if they miss a dose on one day, they must not take any extra dose the next day, but instead contact the study center as soon as possible to ask for advice.

Patients should be instructed to take the study drug as per protocol and instructed to complete the medication diary found in Appendix B, Section **13.2**. All dosages prescribed and dispensed to the patient and any dose change or interruption must be recorded appropriately.

3.3 DOSE MODIFICATIONS

3.3.1 Dose modification and dose delay

3.3.1.1 Dosing modifications

For patients who do not tolerate the protocol-specified dosing schedule, dose adjustments are permitted in order to allow the patient to continue the study treatment.

Abbreviated Title: Phase II everolimus for BHD

Version Date: March 7, 2017

All dose modifications should be based on the worst preceding toxicity. Dose modifications will be made only for those AEs thought to be related to everolimus.

For each patient, once a dose reduction has occurred, the dose level may not be re-escalated during subsequent treatment cycles with everolimus. Dose modifications will follow the scheme outlined in Table 3-1. No more than 2 dose reductions will be allowed per patient.

Table 3-1: Study treatment schedule adjustments and dose levels

Dose level	Dose and schedule*
1	10 mg PO QD
0 (starting dose)	5mg PO QD
-1	2.5mg PO QD

* Once patients have had a dose escalation to the 10mg p.o. QD dose, dose reductions for AEs will be to move to the next lower dose level.

If a patient has already decreased 2 dose levels, no further dose reduction is permitted. Patients who need an additional dose reduction will be required to discontinue everolimus.

Table 3-2 and Table 3-3 list the dosing guidelines for everolimus-related non-hematologic and hematologic toxicities.

Abbreviated Title: Phase II everolimus for BHD

Version Date: March 7, 2017

Table 3-2: Dosing guidelines for everolimus-related non-hematologic toxicities

Toxicity	Action
Non-Infectious Pneumonitis	Please refer to Table 3-4.
AST or ALT elevation	Maintain current dose level
Grade 1 (> ULN - 3.0 x ULN)	
Grade 2 (> 3.0 - 5.0 x ULN)	
AST or ALT elevation	Interrupt everolimus administration until resolution to \leq grade 1 (or \leq grade 2 if baseline values were within the range of grade 2). If resolution occurs \leq 7 days, everolimus should be re-started at the dose level prior to interruption.
Grade 3 (> 5.0 - 20.0 ULN)*	If resolution takes $>$ 7 days, or if event recurs within 28 days, hold everolimus until recovery to \leq grade 1 or baseline grade / value and reintroduce everolimus at one dose level lower, if available.
AST or ALT elevation	Discontinue everolimus.
Grade 4 (> 20 x ULN)*	
Intolerable grade 2 mucositis, or grade 3 AE, except hyperglycemia or hypertriglyceridemia or hypercholesterolemia (see Section 3.3.2.6)	Interrupt everolimus administration until resolution to \leq grade 1 or baseline grade / value. If resolution occurs within \leq 7 days, everolimus should be re-started at the dose level prior to interruption. If resolution takes $>$ 7 days, or if event recurs within 28 days, hold everolimus until recovery to \leq grade 1 or baseline grade / value and reintroduce everolimus at one dose level lower, if available. Patients will be withdrawn from the study if they fail to recover to \leq grade 1 or baseline grade / value within 28 days.
Any other grade 4	Discontinue everolimus.
Grade 3 or 4 clinical liver failure (asterixis or encephalopathy/coma)	Discontinue everolimus
Recurrence of intolerable grade 2 mucositis or grade 3 event after dose reduction	Reduce dose to the next lower dose level, if available. The lowest possible dose level of everolimus is 2.5 mg daily. Below this level, everolimus must be discontinued. If toxicity recurs at Grade 3, consider discontinuation
Any non-hematologic toxicity requiring Everolimus interruption for $>$ 28 days	Discontinue everolimus

Table 3-3 Dosing guidelines for everolimus-related hematologic toxicities

Toxicity	Action
≤ Grade 2 thrombocytopenia (platelets <75, ≥ 50 x10 ⁹ /L)	No action
Grade 3 thrombocytopenia (platelets <50, ≥ 25 x10 ⁹ /L)	Interrupt everolimus until resolution to grade ≤1 If resolution occurs ≤ 7 days, reintroduce everolimus at the dose level prior to interruption. If resolution occurs > 7 days, or event occurs within 28 days, reintroduce everolimus at one dose level lower, if available.
Grade 4 thrombocytopenia (platelets < 25 x10 ⁹ /L)	Discontinue everolimus
Grade 3 neutropenia or anemia (neutrophil <1, ≥ 0.5 x10 ⁹ /L)	Interrupt everolimus until resolution to grade ≤1 or baseline value If AE resolution occurs ≤ 7 days, reintroduce everolimus at the same dose level. If AE resolution occurs > 7 days, or event occurs within 28 days, reintroduce everolimus at one dose level lower, if available.
Grade 4 neutropenia or anemia	Discontinue everolimus
Febrile neutropenia	Interrupt everolimus until resolution to grade ≤ 1 (or baseline value) and no fever. Reintroduce everolimus at one dose level lower, if available.*
Recurrence of grade 3 toxicity after dose reduction	Reduce dose to the next lower dose level, if available. The lowest possible dose level of everolimus is 5 mg every other day (2.5 mg daily). Below this level, everolimus must be discontinued.
*Any hematologic toxicity requiring everolimus interruption for > 28 days	Discontinue everolimus

3.3.2 Management of specific toxicities

Overall, safety data available from completed, controlled and uncontrolled studies indicate that everolimus is generally well tolerated at weekly or daily dose schedules. The safety profile is characterized by manageable adverse events (AEs). These AEs are generally reversible and non-cumulative.

Adverse events most frequently observed with everolimus are stomatitis, rash, diarrhea, fatigue, infections, asthenia, nausea, peripheral edema, decreased appetite, headache, dysgeusia, epistaxis, mucosal inflammation, pneumonitis, weight decreased, vomiting, pruritus, cough, dyspnea, dry skin, nail disorder, and pyrexia. Overall, the most frequently observed laboratory abnormalities include decreased hematology parameters including hemoglobin, lymphocytes, platelets, and neutrophils (or collectively as pancytopenia); increased clinical chemistry parameters including cholesterol, triglycerides, glucose, aspartate transaminases, creatinine, alanine transaminases, and bilirubin; and decreased clinical chemistry parameters including phosphate and potassium. The majority of these AEs have been of mild to moderate severity (NCI CTC grade 1-2).

3.3.2.1 Management of infections

Everolimus has immunosuppressive properties and may predispose patients to bacterial, fungal, viral or protozoal infections, including infections with opportunistic pathogens. Localized and systemic infections, including pneumonia, other bacterial infections, invasive fungal infections,

Abbreviated Title: Phase II everolimus for BHD

Version Date: March 7, 2017

such as aspergillosis or candidiasis and viral infections including reactivation of hepatitis B virus, have been described in patients taking everolimus. Some of these infections have been severe (e.g. leading to sepsis, respiratory or hepatic failure) and occasionally have had a fatal outcome.

Physicians and patients should be aware of the increased risk of infection with everolimus. Treat pre-existing infections prior to starting treatment with everolimus. While taking everolimus, be vigilant for symptoms and signs of infection; if a diagnosis of infection is made, institute appropriate treatment promptly and consider interruption or discontinuation of everolimus.

If a diagnosis of invasive systemic fungal infection is made, discontinue everolimus and treat with appropriate antifungal therapy.

3.3.2.2 Management of skin toxicity

For patients with grade 1 toxicity, no specific supportive care is usually needed or indicated. Rash must be reported as an AE. Patients with grade 2 or higher toxicity may be treated with the following suggested supportive measures at the discretion of the investigator: oral minocycline, topical tetracycline, topical clindamycin, topical silver sulfadiazine, diphenhydramine, oral prednisolone (short course), topical corticosteroids, or pimecrolimus.

3.3.2.3 Renal Failure Events

Cases of renal failure (including acute renal failure), some with fatal outcome, occurred in patients treated with everolimus. Renal function of patients should be monitored particularly where patients have additional risk factors that may further impair renal function.

Elevations of serum creatinine, usually mild, and proteinuria have been reported in patients taking everolimus. Monitoring of renal function, including measurement of blood urea nitrogen (BUN), urinary protein, or serum creatinine, is recommended prior to the start of everolimus therapy and periodically thereafter.

Abbreviated Title: Phase II everolimus for BHD

Version Date: March 7, 2017

3.3.2.4 Management of stomatitis / oral mucositis / mouth ulcers

Adverse Drug Reaction	Severity	Everolimus Dose Adjustment and Management Recommendations
Stomatitis	Grade 1 (Minimal symptoms, normal diet)	No dose adjustment required. Manage with non-alcoholic or salt water (0.9%) mouth wash several times a day.
	Grade 2 (Symptomatic but can eat and swallow modified diet)	Temporary dose interruption until recovery to grade ≤ 1 . Re-initiate everolimus at the same dose. If stomatitis recurs at grade 2, interrupt dose until recovery to grade ≤ 1 . Re-initiate everolimus at a lower dose. Manage with topical analgesic mouth treatments (e.g. benzocaine, butyl aminobenzoate, tetracaine hydrochloride, menthol or phenol) with or without topical corticosteroids (i.e. triamcinolone oral paste)*.
	Grade 3 (Symptomatic and unable to adequately eat or hydrate orally)	Temporary dose interruption until recovery to grade ≤ 1 . Re-initiate everolimus at lower dose. Manage with topical analgesic mouth treatments (i.e. benzocaine, butyl aminobenzoate, tetracaine hydrochloride, menthol or phenol) with or without topical corticosteroids (i.e. triamcinolone oral paste)*
	Grade 4 (Symptoms associated with life-threatening consequences)	Discontinue everolimus and treat with appropriate medical therapy.

* using agents containing alcohol, hydrogen peroxide, iodine, and thyme derivatives in management of stomatitis as they may worsen mouth ulcers.

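### Table 3-2 and Section 3.3.2.4 give opposite restart doses in two first-event stomatitis situations, and Sections 3.1 and 3.4 disagree on stopping at week 52 in locally advanced disease

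*Combined protocol and SAP*

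**What the plan says.** **Restart dose, Table 3-2 (Section 3.3.1.1).** One row covers "Intolerable grade 2 mucositis, or grade 3 AE, except hyperglycemia or hypertriglyceridemia or hypercholesterolemia". If the event resolves in 7 days or less, "everolimus should be re-started at the dose level prior to interruption". If it takes longer, or recurs within 28 days, the instruction is to hold and then "reintroduce everolimus at one dose level lower, if available. Patients will be withdrawn from the study if they fail to recover" within 28 days. A further row covers "Recurrence of intolerable grade 2 mucositis or grade 3 event after dose reduction". It moves the patient to the next lower level if there is one, and adds: "The lowest possible dose level of everolimus is 2.5 mg daily. Below this level, everolimus must be discontinued". It also says: "If toxicity recurs at Grade 3, consider discontinuation".

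**Restart dose, Section 3.3.2.4.** After a first grade 2 event: "Re-initiate everolimus at the same dose. If stomatitis recurs at grade 2", the dose is interrupted again and restarted lower. After grade 3: "Re-initiate everolimus at lower dose. Manage with topical analgesic mouth treatments". Neither row refers to the time taken to recover.

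**Dose levels (Table 3-1 and Section 3.3.1.1).** The levels are 10, 5 (starting dose) and 2.5 mg daily. At most two reductions are allowed, and a reduced dose may not be raised again.

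**Duration.** Section 3.1 limits treatment to 52 weeks and exempts only metastatic RCC. Section 3.4 limits kidney-localized tumors to one year and treats both locally advanced and metastatic disease until progression. Section 2.1.1 makes localized, locally advanced and advanced tumors eligible.

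**The concern.** Table 3-2 keys the restart dose to time. Section 3.3.2.4 keys it to grade and recurrence. Both cover stomatitis, and no sentence says which governs. Table 3-2 sends pneumonitis to Table 3-4 and metabolic events to Section 3.3.2.6, but it has no such pointer for mucositis, which it names in its own rows.

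The choice of text changes what a patient receives. Because reductions are permanent and 2.5 mg is the lowest level, a patient on the 5 mg starting dose either keeps one level in reserve or has none. The next event that calls for a reduction then means 2.5 mg under one text and discontinuation under the other. Section 3.3.2 lists stomatitis among the most frequent everolimus adverse events, so the situation is foreseeable.

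The duration mismatch is a separate matter. A locally advanced, non-metastatic patient who is progression-free on drug at week 52 stops under Section 3.1 and continues under Section 3.4.

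**Working it through.** The check is a comparison of texts; no sample-size or error-rate figure is involved.

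**Step 1. Restart dose, first stomatitis event, no earlier dose reduction.**

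| Situation | Table 3-2 | Section 3.3.2.4 | Result |
|---|---|---|---|
| Intolerable grade 2, 7 days or less | same | same | agree |
| Intolerable grade 2, 8 to 28 days | one level lower | same | **conflict** |
| Grade 3, 7 days or less | same | lower | **conflict** |
| Grade 3, 8 to 28 days | one level lower | lower | agree |
| Grade 4 | discontinue | discontinue | agree |

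That gives two conflicts, running in opposite directions: Section 3.3.2.4 is stricter for short grade 3 events and Table 3-2 is stricter for prolonged intolerable grade 2. Neither text is consistently the cautious one. Beyond 28 days, Table 3-2 discontinues for any non-hematologic toxicity. Section 3.3.2.4 sets no time limit of its own, so I read it as subject to that row.

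**Step 2. Size of each restart difference.** Inputs are the Table 3-1 levels.

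- On 5 mg: same dose is 5 mg, lower dose is 2.5 mg; ratio 5 / 2.5 = 2. Levels left below the restart dose: 1 (2.5 mg) versus 0.
- On 10 mg: same dose is 10 mg, lower dose is 5 mg; ratio 10 / 5 = 2. Levels left: 2 (5 and 2.5 mg) versus 1 (2.5 mg).

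The 5 mg case applies to events before the first restaging at about 12 weeks. Everyone is then on the starting dose, and Section 3.1 does not escalate a patient who has had attributable toxicity of grade 2 or more.

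**Step 3. Duration, patient progression-free and on treatment at week 52.**

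| Disease extent | Section 3.1 | Section 3.4, by disease extent | Result |
|---|---|---|---|
| Localized to kidneys | stop | stop | agree |
| Locally advanced, non-metastatic | stop | continue | **conflict** |
| Metastatic | continue | continue | agree |

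That gives one conflict: 52 weeks versus open-ended treatment.

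**The case against.** The strongest reply is that these texts guide rather than bind. Table 3-2 is introduced as guidelines, Section 3.3.2.4 is headed as recommendations, and Section 3.3.1.1 describes dose adjustments as permitted. A specific-over-general reading would also settle both cases. For a short grade 3 event, the stomatitis row is more specific than a generic grade 3 row. For prolonged intolerable grade 2, Table 3-2 is more specific because it adds intolerability and duration. One team treats at most 18 patients and could agree on this informally.

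Much of this stands, and it keeps the point minor. It does not remove it. No sentence states that reading, and a clinician who opens only one of the two tables gets the opposite dose.

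Three stronger readings are tempting, and the documents do not support them:

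- **Every grade 2 stomatitis is in conflict.** Table 3-2 addresses only intolerable grade 2. Where it means dosing to continue, it says so, as for grade 1 and 2 AST/ALT elevation. It is silent on tolerable grade 2, and Section 3.3.2.4 fills that gap.
- **Each such restart is a reportable deviation.** Section 7.1.8 defines a deviation as a departure from the approved protocol, and Section 7.3.1 makes deviations reportable. Restarting exactly as one approved table directs is hard to call a departure, and neither section says that choosing between two approved texts is one.
- **The unqualified 52-week sentences in Sections 3.4 and 6.2 are further conflicts.** They omit even the metastatic exception, on which Sections 3.1 and 3.4 agree, so they read as shorthand.

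**Conclusion.** Wrong as written, minor in scope. There are two first-event situations with opposite restart doses, each a two-fold and irreversible difference, and one duration conflict confined to locally advanced, non-metastatic patients who are progression-free on treatment at week 52. The duration conflict may affect nobody. The protocol gives no stomatitis rate by grade and time to recovery, so the number of patients affected is not estimated; Section 8 caps accrual at 18, and Section 3.3.2 says most everolimus adverse events have been grade 1 or 2.

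The restart count assumes a first stomatitis event in a patient on 5 or 10 mg with no earlier reduction.

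A reader might infer that the trial's inference is damaged. It is not: the two-stage design, sample size, power and response threshold in Section 8 depend on none of these rules.

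**What to change.** 1. **Stomatitis.** Make Section 3.3.2.4 the only rule for stomatitis and oral mucositis, and have the interruption and recurrence rows of Table 3-2 point to it, as that table already points elsewhere for pneumonitis and metabolic events. Simply handing control to the present Section 3.3.2.4 would loosen dosing for prolonged intolerable grade 2, so carry the more cautious instruction into it for each conflict:
   - Grade 3: restart one level lower, whatever the time to recovery.
   - First grade 2: restart at the same dose, except that intolerable grade 2 taking more than 7 days to resolve restarts one level lower.
   - Recurrence: next lower level if available, with 2.5 mg daily as the floor and discontinuation below it; keep the advice to consider stopping if toxicity recurs at grade 3.
   - Interruption longer than 28 days: discontinue, as now.

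2. **Duration.** Extend the Section 3.1 exception from metastatic RCC to locally advanced or metastatic RCC, and qualify the general 52-week sentences in Sections 3.4 and 6.2 to match. If the sponsor does intend a 52-week cap for locally advanced disease, amend Section 3.4 instead.

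**Cost.** Protocol wording only, with no added patients, visits or procedures. The downside is slightly lower dose intensity. After a short grade 3 event or a prolonged intolerable grade 2 event the reduction is permanent, and a patient on 5 mg then has no level left below 2.5 mg. That is the reasonable side to err on, since Section 3.1 notes that most of these patients have a surgical option and are less willing to accept side effects than patients with metastatic disease.
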